23.4 Inclusion in analysis

The principal analysis will be performed on the as-randomised ("intention to treat") population, analysing participants with available outcome data in their randomised groups, regardless of adherence. Secondary populations will also be analysed as defined in Section 23.3.

The study will be reported in line with CONSORT guidelines.

23.5 Subgroup analysis

Secondary subgroup analyses of the primary outcome will investigate visually, presenting using forest plots, whether treatment effects vary by the key clinical factors (baseline KOOS-4 level, and planned lateral extra-articular procedure, and age group (<20 years, 20 years and over).

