23.2 Sample Size/Power Calculations

The sample size calculation was premised upon a 1:1 randomised parallel group trial design with an analysis of the primary outcome (KOOS-4) using mixed-effects linear model adjusted for randomisation variables and baseline KOOS-4. Standard nominal 2-sided 5% significance level was adopted, and the power for detecting a between group difference of 8 and 9 points in the KOOS-4, was assessed for a missing data allowance of 15%.

We considered a variety of scenarios varying the adjustment for baseline correlation and desired statistical power. (See Table 4 below for a selection)

Table 4 – Sample size scenarios; all based upon 2-sided 5% significance level, 1:1 allocation continuous outcome, pooled SD of 20, and non-central-t distribution calculation [Stata power two means command]

No.	Target difference	Statistical Power	Missing data allowance	Adjusted for baseline	Sample size required (overall)
1	8	80	15%	No	236
2	8	90	15%	No	314
3	9	80	15%	No	186
4	9	90	15%	No	248
5	8	80	15%	Yes	204
6	8	90	15%	Yes	272
7	9	80	15%	Yes	162
8	9	90	15%	Yes	214

An overall sample size of 236 and 186 is required for 80% power for a difference of 8 points and 9 points respectively given a pooled standard deviation (SD) of 20 points. Equivalent 90% power, required number of observations are 314 and 248 respectively.

However, the expected sample size required is lower given the planned adjustment for baseline KOOS-

4 score as the effective variability is reduced. Implementing this using the formula provided by Borm⁽³⁹⁾ using a correlation between baseline and follow-up score of 0.37 leads to requiring only 204 and 272 for 80% and 90% power for a target difference of 8 points or equivalently 162 and 214 (all other assumptions and inputs as before) for 9 points difference. Therefore, we have opted for a sample size of 214 (no. 8, table 2) randomised participants which allows for 15% missing data for a target difference of 9 points (at 90% power). This sample size also ensures more than 80% power for a target difference of 8 points (no. 5, Table 2).

We anticipate that 25% of those who consent to be assessed as unsuitable for repair intra-operatively, we expect approximately 286 will need to be consented. The intraoperative assessment at arthroscopy has been shown to be crucial to determine the repairability of the ligament and reduce failure rate $^{(40)}$.

Justification of sample size inputs

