23.3 Description of Statistical Methods

The statistical analyses will be performed once the 24 months follow up has been reached by the last patient and sufficient time has been allowed for data collection and cleaning.

Results will be reported in line with the Consolidated Standards of Reporting Trials (CONSORT) statement and any appropriate extensions and will be described fully in a separate Statistical Analysis Plan. The SAP will be finalised prior to un-blinding of the data to clinical investigators and after consultation with investigators and other relevant stakeholders.

Nominal 2-sided 5% significance level will be used throughout. Subgroup analyses will be indicated as exploratory and non-planned analyses as "post-hoc".

Intention-to-treat (ITT) will be the main analysis strategy and will be adopted for the primary and all secondary outcomes. In other words, the analysis will principally be focussed on a treatment policy estimand. As patients are randomised in theatre, following surgeon confirmation of suitability, non-compliance is expected to be minimised and intercurrent events more limited than in a typical NHS based surgical study (e.g. no post-randomisation timing of surgery mediation). However, some repairs may still be abandoned, perioperatively and post randomisation. Rates of compliance will be monitored throughout the study, including the pilot phase. Two secondary analysis populations will therefore be conducted on the primary outcome: a per-protocol analysis, that mirrors ITT but excludes patients with major protocol deviations, and an as-treated analysis, where patients are classified according to the treatment received. These secondary analyses will assess robustness of ITT analysis and any deviation from routine clinical practice. The handling of such events will be agreed in advance of conducting the analysis and detailed in the SAP.

The main analysis will be conducted using a complete case approach with no planned imputation for missing data. An independent Data and Safety Monitoring Committee (DSMC) will meet early in the study to agree its terms of references. They will review confidential interim analyses of the stop-go criteria and monitor within patient correlation of KOOS-4 scores between baseline and 24 months and compliance to randomised treatment.

It is anticipated that all statistical analysis will be undertaken using Stata (StataCorp LP, www.stata.com) or other validated statistical software.

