23.3.1 Primary outcome

The primary outcome (KOOS-4 at 24 months) will be compared using a mixed-effects linear model to calculate the mean difference between treatment groups. Treatment, baseline KOOS-4 and planned lateral extra-articular procedure will be incorporated as fixed effects and recruiting site as a random effect. Results will be presented as estimates and 95% CIs whenever possible. A sensitivity analysis will be conducted that removes participants aged 20 years or younger at the time of completing baseline KOOS-4. Sensitivity to missing data will also be explored using informative missing to confirm tolerance to differential mechanisms (using a pattern-mixture model approach).

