23.7 Level of Statistical Significance

All treatment comparisons will be reported with 95% confidence intervals and a significance level of 5% will be used to test statistical significance.

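### Exploratory subgroup effects are to be judged by eye from forest plots with no interaction estimate named; separately, a minor slip puts 20-year-olds on different sides of the age line in two analyses

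*Protocol*

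**What the plan says.** Section 23.5 (Subgroup analysis) states that secondary subgroup analyses of the primary outcome "will investigate visually, presenting using forest plots, whether treatment effects vary by the key clinical factors". It lists three factors: baseline KOOS-4 level, planned lateral extra-articular procedure, and "age group (<20 years, 20 years and over". No treatment-by-factor interaction is named there or elsewhere. The nearest thing is the time-by-treatment term for repeated secondary outcomes in section 23.3.2.

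Three other sections bear on the point:

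- Section 23.3 says that subgroup analyses will be labelled exploratory, and section 10.9 uses the same description.
- Section 23.7 says: "All treatment comparisons will be reported with 95% confidence intervals and a significance level of 5% will be used to test statistical significance".
- Section 23.3.1 plans a sensitivity analysis of the primary outcome that "removes participants aged 20 years or younger at the time of completing baseline KOOS-4". Section 23.5 does not say at what date age is taken.

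**The concern.** Section 23.5 asks whether the treatment effect differs between subgroups. That is a question about one quantity, the difference between two subgroup effects, and its uncertainty. A forest plot of separate subgroup estimates does not show this quantity directly, and visual reading has no stated criterion. In a trial sized for the overall effect, subgroup estimates will often lie far apart by chance. A reader may then take a gap as evidence of effect modification, or dismiss a gap that is compatible with a large one. This is not just detail left to the SAP, because the protocol itself fixes visual inspection as the method.

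The age rules raise a smaller, separate matter. The sensitivity analysis and the age subgroup both divide participants at about 20 years, but they divide them differently and no reason is given. The sensitivity population and the older subgroup are therefore not the same people, although they are likely to be reported close together.

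**Working it through.** **Inputs.** From section 23.2 and Table 4: two-sided 5% level, 1:1 allocation, SD 20, baseline correlation 0.37, target difference 9, power 90%, 15% missing, 214 randomised. The split between subgroup levels is not in the protocol. It is an assumption, shown as a range.

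**The plan's own figure.** The non-central t calculation for a difference of 9 with SD 20 and 90% power gives 105 per arm. Baseline adjustment multiplies this by 1 − 0.37² = 0.8631, giving 90.6 per arm. Allowing for 15% missing, 2 × 90.6 / 0.85 = 213.2, which rounds up to the even number 214. The stated sample size is reproduced.

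**Precision of the overall effect.**

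- Analysed: n = 214 × 0.85 = 181.9.
- Residual variance: 400 × 0.8631 = 345.2, so the residual SD is 18.58.
- SE of the overall effect: 2 × 18.58 / √181.9 = 2.755 points.

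**Precision of a difference between subgroup effects.** Let the smaller level hold a share f, with equal allocation within levels. Then

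SE(interaction) = √[4 × 345.2 / (n f) + 4 × 345.2 / (n (1 − f))] = 2.755 / √[f (1 − f)].

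The chance of a gap of 9 points or more with no true interaction is 2 × [1 − Φ(9 / SE)]. The power column is for a true 9-point interaction tested at the two-sided 5% level.

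| Assumed split | SE (points) | 95% CI half-width | Chance gap of 9 or more | Power |
|---|---|---|---|---|
| 50:50 | 5.51 | 10.8 | 10.2% | 37% |
| 30:70 | 6.01 | 11.8 | 13.4% | 32% |
| 20:80 | 6.89 | 13.5 | 19.1% | 26% |

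A more uneven split is worse: at 10:90 the SE is 9.18 and the power 17%. An interaction would have to be about 15.4 points at 50:50, or 19.3 at 20:80, to be detected with 80% power (2.80 × SE).

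**The age rules side by side, in completed years.**

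| Age | Sensitivity analysis (23.3.1) | Subgroup (23.5) |
|---|---|---|
| 19 | removed | younger |
| 20 | removed | older |
| 21 | kept | older |

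The sensitivity population is 21 and over, and the older subgroup is 20 and over. Only 20-year-olds are treated differently. The reference date can matter too. Section 23.3.1 takes age when baseline KOOS-4 is completed, while section 10.8 allows about a month between consent and randomisation, so a birthday can fall between the two.

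**The case against.** The strongest reply is that these analyses are declared exploratory, so no confirmatory decision rests on the plot. Also, section 23.7 requires confidence intervals for all treatment comparisons, so the imprecision of each subgroup estimate should be visible. An interaction estimate would itself have low power and would seldom settle whether effects vary. The SAP, not shown here, may add one. All of this stands, and it limits the weight of the point. It does not remove it. The interval for the difference is not read directly from two separate intervals, and a wide interval for the interaction tells the reader plainly that the trial cannot distinguish the subgroups.

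Some stronger readings should not be drawn:

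- *The protocol rules out an interaction estimate.* It does not. It names none.
- *Readers will be misled by one interval excluding zero and the other not.* With a uniform true effect of 9, this would occur in about 46% (50:50) to 63% (20:80) of trials. But the protocol sets no rule of reading the plot that way, and the same intervals would remain after the fix.
- *Adolescents were included because the effect is expected to differ by age.* Sections 8.1 and 11.5 give clinical uncertainty, generalisability, high re-rupture rates, potential benefit and surgeon equipoise. They do not state an expected difference in treatment effect.
- *The sensitivity analysis was meant to be an adult population equal to the older subgroup.* The protocol does not say so, and from age 16 participants sign the adult consent form (section 14.1).
- *Baseline KOOS-4 will certainly be cut into categories.* This is a fair inference from the word level and the forest-plot format, but no cut is stated.

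**Conclusion.** The point holds as a reporting weakness in exploratory analyses. The protocol chooses visual judgement for a question that has a direct estimate, and chance alone would separate two subgroup estimates by at least the trial's own 9-point target difference in about 10% to 19% of trials. That range rests on the protocol's SD, correlation and missing-data allowance, on equal allocation within levels, on a common residual SD, and on assumed splits between 50:50 and 20:80. Site effects are ignored.

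The age mismatch is real but minor. It concerns only 20-year-olds, in one sensitivity analysis and one subgroup factor, and its effect on the estimates cannot be sized because the protocol gives no age distribution. Neither matter touches the primary analysis or the sample size of 214.

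**What to change.** In section 23.5, and in the SAP, add treatment-by-factor interaction terms to the primary mixed model, one factor at a time. Report each interaction estimate with its 95% CI beside the forest plot, labelled exploratory and low-powered. Baseline KOOS-4 and planned lateral extra-articular procedure are already main effects in that model; the age analysis also needs a main effect of age group. Preferably base the baseline KOOS-4 interaction on the continuous score and use any categories only for display.

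For age, use one boundary and one reference date in sections 23.3.1 and 23.5, or state why they differ.

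The cost is a few sentences and a few extra model terms. No new data, participants or change to the primary analysis are needed.

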23.6 Interim analyses

The main outcomes will be analysed as stated in the analysis plan once the study follow-up has been completed. No formal interim analyses of treatment effect are planned for any of the study outcomes.

23.6.1 Stopping rules

As no formal interim analyses are planned, no stopping rules have been incorporated into the study design. An independent Data and Safety Monitoring Committee* (DSMC) will review the accumulating

data at regular intervals and may recommend pausing or stopping the study in the event of safety concerns.

23.7 Level of Statistical Significance

All treatment comparisons will be reported with 95% confidence intervals and a significance level of 5% will be used to test statistical significance.

23.8 Procedure for accounting for missing data

The procedure for handling spurious or missing data will be described in the SAP. The study will attempt to collect data as completely as possible. The sample size calculation incorporated an inflation to account for potential loss to follow-up.

23.9 Procedures for reporting any deviation(s) from the original statistical analysis plan

Any deviation(s) from the original SAP will be described in the final statistical report.

23.10 Internal pilot/Decision Points

An internal pilot is planned that will progress seamlessly to the definitive study if all predefined progression criteria are reached. The embedded pilot phase will take place in UK sites with staggered initiation over a period of 10 months. Screening and recruitment to this study will occur in 2 phases. Patients will be identified and screened at A&E, virtual fracture clinics, and orthopaedic outpatient clinics and then will be invited to participate following confirmation of eligibility criteria. Randomisation will occur in theatre following a final eligibility check.

The recruitment rate will account for the time lag between patient consent and randomisation in theatre (therefore, no participants will be randomised in month 1), and for patients identified as not eligible in theatre and not randomised. Overall patient recruitment target for this internal pilot phase will be 28 randomised patients.

The internal pilot study will mirror the procedures and logistics undertaken in the main definitive study. It is intended that the study will progress seamlessly into the main phase.

Data from the internal pilot study will contribute to the final analysis. The purpose of the internal pilot is to assess the feasibility of site and test and refine the patient recruitment process. We will collect data on the number of patients screened, assessed for eligibility and randomised to determine the feasibility of the main trial. The decision to progress to the main trial will be made in collaboration with the TSC and NIHR HTA programme based on the pre-defined progression criteria. Progression to the main trial, will be informed using the traffic light system recommended by Avery⁽⁴⁶⁾ in terms of the decision-making process for stopping (red), amending the trial (amber) or proceeding (green) to a main trial. The internal pilot will also identify how well the sites are able to accommodate the delivery of our interventions within their existing pathways and workloads.

Stop-go criteria will be reviewed after 10 months of recruitment.

Stop-amend-go criteria for the pilot phase are given in Table 5 together with the definitions of how each will be measured.

Table 5: Stop-amend-go criteria for internal pilot phase.

	Red	Amber	Green
Progression criteria	(Stop)	(Amend)	(Go)
Total number of participants recruited (randomised)	<17	17-27	28
Study recruitment (randomisation)	<60%	60-99%	100%
Recruitment (randomisation) rate/site/month*	<0.5	0.5-0.75	>0.75
Number of sites opened	<5	5-8	9

NB: * Individual sites will vary, and indicative figures are means across all active sites

The Trial Management Group (TMG) will closely monitor the progression criteria during the internal pilot, and together with the Trial Steering Committee (TSC) and Data and Safety Monitoring Committee (DSMC) will perform a full review towards the end of the internal pilot. The TSC and funder would make the final decision to terminate the study.

24 HEALTH ECONOMICS

Cost Utility analysis

As with the statistical analysis, a detailed health economic analysis plan (HEAP) with full details of all analyses will be drafted early in the study and finalised prior to primary outcome analysis. The HEAP will be reviewed and will receive input from the Trial Steering Committee (TSC) and DSMC.

An economic evaluation will compare resource use, costs and health-related quality of life of ACL repair relative to ACL reconstruction following an intention-to-treat principle. The perspective of the analysis will be of the NHS and personal social care services. In sensitivity analysis, we will consider a societal perspective. The primary health economics outcome measure used in the study will be incremental cost per quality-adjusted life year (QALY). The health-related quality of life instrument EQ-5D-5L collected at baseline, 6-, 12- and 24-months follow-up will provide utility values for the calculation of QALYs. The valuation of EQ-5D-5L responses will follow the latest guidance from NICE's manual for health technology evaluations⁽⁴⁷⁾.

Direct treatment-related NHS resource use data including intervention (ACL repair and reconstruction), re-operations and re-admissions, physiotherapy sessions, adverse events, primary care and outpatient contacts will be identified and collected using patient questionnaires at 6-, 12- and 24-months follow-up complemented by hospital records, where appropriate. The questionnaires will build on the design, content and approach used in the ACL SNNAP study to enhance retention and response rates. The patient questionnaires will also collect information on lost earnings because of the knee injury, school or university absence due to knee injury and the use of private healthcare services. Resource use data will be costed using national average unit costs^(48, 49).

Descriptive statistics (means, SD as minimum) will be reported for resource use, costs, and EQ-5D-5L utilities at each follow-up time point using complete data. Differences between study arms will be

estimated using mixed effects linear regression models to allow for multiple follow-ups clustered within participants. Missing data will be addressed following best practice in cost-effectiveness studies⁽⁵⁰⁾. Mean imputation of baseline data and multiple imputation of follow-up costs and EQ-5D-5L values will be undertaken, if found to be appropriate after examining the patterns of missing data. Hence, we will use predictive mean matching to create a total number of imputed datasets as the proportion of data missing across all time periods.

Following multiple imputation, total costs and QALYs will be estimated for all participants in the study and discounted at the recommended 3.5% rate. On each imputed dataset, we will estimate incremental costs and QALYs using separate linear regression models controlling for treatment allocation and other variables. These estimates will be combined using Rubin's rule to produce the mean difference in costs and QALYs of ACL repair relative to ACL reconstruction. Incremental cost-effectiveness ratio (ICER) will be estimated by dividing the difference in costs by the difference in QALYs of the two treatments under analysis and will be depicted on the cost-effectiveness plane. This will be interpreted as the additional costs/savings associated with the additional QALY benefits from doing ACL repair compared with ACL reconstruction. The joint uncertainty around incremental costs and QALYs will be estimated using bootstrapping from each imputed dataset, running the estimation model and extracting the estimated treatment effects. From the bootstrap results, we will produce confidence intervals for the difference in costs and QALYs and estimate a cost-effectiveness acceptability curve informing the probability of the ACL repair being cost-effective at different maximum willingness to pay values, e.g. £20,000 to £30,000 per QALY gained.

Informed by the data from this study, we will also undertake a modelling exercise to explore the budget impact of promoting an accelerated pathway for ACL injuries, with early repair and reconstruction, compared to current practice as assessed in studies such as the ACL SNNAP study.

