5 LAY SUMMARY/PLAIN ENGLISH SUMMARY

The knee is the most injured joint. The Anterior Cruciate Ligament (ACL) is an important band of tissue that supports the knee. It is a strong structure in the centre of the knee which attaches the femur (thigh bone) to the tibia (shin bone). It is often injured during manual work or sports. Injury to the ACL can lead to the knee becoming unstable, giving way and a loss of confidence. An unstable knee can cause damage to other parts of the knee such as the cartilage or meniscus (shock absorbers), which can lead to osteoarthritis (OA) developing in later life.

There are different surgical options for people with an ACL injury. The most common is reconstruction, which uses tissue from other parts of the body, such as the hamstrings, to act as a replacement. This is a successful operation but does involve damage to bones from drilling holes, removal of tissue from elsewhere in the body, and does not keep any of the torn ligament which has potentially useful nerve endings. An alternative approach is to reattach the original ligament back from where it has torn in a "repair" rather than reconstruction. By preserving the ligament, avoiding tissue harvest and bone drilling, ACL repair could provide faster recovery, better medium to long term stability, and might reduce likelihood of OA in the future. Older versions of ACL repair techniques have not worked well enough, but newer techniques are available, and this may now make repair a viable option.

What do we want to find out?

Modern ACL repair (stitching) is relatively new and, despite clear potential, has not been fully evaluated. It remains unknown whether it confers any of the theoretical benefits. We aim to conduct a comparative study to find out which is the best technique, reconstructing the ligament or repairing it. The research question is: For patients with recent proximal ACL ruptures (where the ligament has pulled directly off the bone), is ACL repair superior to ACL reconstruction at 24 months post-surgery? This will be measured by a questionnaire relating to the knee called KOOS-4.

How are we going to do this?

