ACL Repair: is a surgical technique to reattach the detached ligament from its footprint on the femur. It has been shown to be possible in specific patterns of tear where the length of the damaged ligament is preserved, the tear is close to the femoral attachment and the gross structure of the ligament has been maintained. These features can be assessed pre-operatively on MRI scan and may be present in up to 43% of tears⁽⁵⁾. Time to surgery has been determined as a key factor in the success of ACL repair. Ideally, surgery must be undertaken as soon as possible, to maintain healing potential after the repair⁽⁶⁾. ACL repair is used by some surgeons in the UK but is not yet widely accepted, as evidence for benefit and value remains limited. This study will allow ACL repair to be evaluated in a safe and robust fashion, as recommended by the IDEAL (Idea, Development, Exploration, Assessment, Long-term study) framework for the investigation of surgical procedures⁽⁷⁾. The study has the support of the orthopaedic surgical community, via the British Association of Surgery for the Knee (BASK), British Orthopaedic Sports Trauma and Arthroscopy Association (BOSTTA) and British Society for Children's Orthopaedic Surgery (BSCOS). ACL repair takes a similar amount of surgical skill and theatre time as ACL reconstruction.

ACL reconstruction: is the current gold standard treatment following an ACL injury, in which the old damaged/torn ACL is removed and replaced by a graft. The graft is usually the patient's own tissue that is excised and repurposed to reconstruct the damaged ligament, typically taken from the patient's hamstrings (semitendinosus and gracilis) or Patella Tendon in which a strip of bone and the central third of the patella tendon is used (BTB). Bone tunnels are drilled within the patient's femur and tibia to accommodate the graft that is threaded across the knee.

Theoretical benefits of repair over reconstruction

ACL repair preserves the native tissue and is a less invasive surgery than reconstruction. Surgical repair eliminates the need for the harvest of other graft tissues, which can cause pain, muscle weakness, altered mechanics and loss of strength for at least two years following surgery⁽⁸⁾. For these reasons, ACL repair has the potential for fewer surgical complications, and faster return to normal range of

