17.2.2 Follow-up assessments/subsequent visits

Follow up for study purposes will be by patient self-reported questionnaire completed using a web-based data collection system (REDCap). The option of being able to fill out the follow-up questionnaires in a hard copy and returning via post will also be available. The questionnaires will contain the following outcome measures: KOOS, EQ-5D-5L/VAS, emotional functioning questions taken from KQoL-26, Tegner, and will be sent out at 6-, 12- and 24-months post randomisation to all participants. Patient satisfaction and return to sport outcome measures will be added to the 12- and 24-month questionnaires. The questionnaires will also ask participants if they have returned to see a health care professional or been admitted to hospital in relation to complications with their study knee, and time away from paid employment and education. The central CTU study team will follow up any complications reported by participants with the research team at the participant's local hospital. Further details about the event will be collected and recorded on a complications form.

A final readmission checklist will be undertaken by the Research staff on hospital records at 24 months post randomisation to ensure that all complications data is collected from all participants (i.e. those who had not returned a questionnaire). Data from any readmission events identified will be recorded in a "Complications" CRF. The physiotherapy case report form (PCRF) will be used to record the number of post-operative rehabilitation physiotherapy sessions attended, and the date of discharge from physiotherapy. If a participant attends community-based physiotherapy, the number of sessions attended will be reported via the patient questionnaires.

Patients will also be asked to complete a pain numerical rating scale to report their post operative pain at 3- and 6-weeks post randomisation. A link to complete the score online will be sent by either SMS, email or post. Contact preferences will be recorded in REDCap after consent.

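### Utility is not measured between randomisation and 6 months, so a quality-of-life difference that has gone by 6 months adds nothing to the incremental QALY

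*Protocol*

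**What the plan says.** The research question in protocol section 9.1 asks about clinical superiority and about cost-effectiveness. Section 24 makes incremental cost per QALY the primary economic outcome and fixes its inputs: "EQ-5D-5L collected at baseline, 6-, 12- and 24-months follow-up will provide utility values for the calculation of QALYs". Table 1 in section 17.1 shows the same schedule. Section 17.2.1 places the baseline questionnaire before randomisation, and section 15 places randomisation in theatre.

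Section 17.2.2 says that the follow-up questionnaires, which carry the EQ-5D-5L, "will be sent out at 6-, 12- and 24-months post randomisation to all participants". The only patient-reported measure scheduled in between is pain: "Patients will also be asked to complete a pain numerical rating scale to report their post operative pain at 3- and 6-weeks post randomisation". Section 10.2 has this collected by SMS link, email link or post.

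On the expected advantages, section 5 says: "By preserving the ligament, avoiding tissue harvest and bone drilling, ACL repair could provide faster recovery". The same sentence goes on to stability and to a lower likelihood of osteoarthritis. Section 8 says "ACL repair has the potential for fewer surgical complications, and faster return to normal range of" movement and activity, and also: "Surgical repair eliminates the need for the harvest of other graft tissues, which can cause pain, muscle weakness". That last sentence continues with changes in mechanics and strength that persist for two years or more.

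**The concern.** If repair does speed recovery, part of the benefit may fall in the first weeks and months, as less pain, better mobility and an earlier return to usual activities. The EQ-5D-5L covers these domains, but it is taken only before the operation and then at 6 months. A QALY built from those points joins the pre-operative injured state directly to month 6. A post-operative dip common to both arms cancels in the comparison. A difference between the arms in the depth or length of that dip does not cancel, and it goes unseen if it has closed by month 6. The same holds for an early disadvantage of repair.

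The health economic analysis plan cannot repair this later. It can choose an interpolation method, and the multiple imputation in section 24 can fill in missed questionnaires, but neither supplies utilities that were never scheduled. The retrospective pre-injury EQ-5D in Table 1 says nothing about recovery, and section 24 does not use the pain score for QALYs.

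**Working it through.** **Plan's own figure.** The protocol gives no QALY or utility figure, so there is none to reproduce. The 214 in Table 4 concerns KOOS-4 and is not in question.

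**Inputs from the protocol.** Utility times are 0, 0.5, 1 and 2 years (section 24). The expected between-arm difference at time 0 is zero (section 17.2.1). Willingness to pay is £20,000 to £30,000 per QALY (section 24).

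**Assumptions.** Linear interpolation (trapezoid rule), since section 24 names no method. A peak utility gap d of 0.03 to 0.10 at week 6, since the documents give none. Simple shapes for how the gap closes.

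**1. What the planned schedule captures.** With differences D0, D6, D12 and D24 at the four visits:

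incremental QALY = 0.5(D0 + D6)/2 + 0.5(D6 + D12)/2 + 1.0(D12 + D24)/2 = 0.25·D0 + 0.5·D6 + 0.75·D12 + 0.5·D24.

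D0 is zero in expectation. If the gap has closed by month 6 and stays closed, the other three are zero too, so the result is 0 whatever d was.

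**2. Size of what is missed.** For a gap rising linearly from 0 to d at week 6 and falling linearly to 0:

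- Closed by week 26: area = 0.5 × (26/52) × d = 0.25d. For d = 0.03 this is 0.0075 QALY (£150 to £225). For d = 0.10 it is 0.025 QALY (£500 to £750).
- Closed by week 13: area = 0.5 × (13/52) × d = 0.125d, which is 0.00375 to 0.0125 QALY (£75 to £375).

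**3. Gaps that outlast month 6.**

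| Shape | True area | Planned schedule | Captured |
|---|---|---|---|
| Peak week 6, zero at 9 months | 0.375d | 0.5 × 0.394d = 0.197d | 53% |
| Peak week 6, zero at 12 months | 0.5d | 0.5 × 0.565d = 0.283d | 57% |
| Held from week 6 to month 6, zero at 12 months | 0.692d | 0.5 × d = 0.5d | 72% |

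The month-6 values come from the straight lines: (0.75 − 0.5)/(0.75 − 6/52) = 0.394 and (1 − 0.5)/(1 − 6/52) = 0.565.

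**4. What a 6-week point adds.** For a gap that is zero at month 6, the trapezoids give 0.5 × (6/52) × d + 0.5 × (20/52) × d = 0.25d.

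- True closure linear to week 26 (0.25d): 100% recovered.
- True closure by week 13 (0.125d): 200%, a twofold overstatement.
- Gap held from week 3 to month 3, then gone by month 6 (true 18/52 × d = 0.346d): 0.25/0.346 = 72%. Adding the 3-week contact as well gives 14.5/52 × d = 0.279d, or 81%.

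A further point at 3 months recovers all three of these shapes in full when it is added to the 3- and 6-week points.

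**The case against.** The strongest reply is that the protocol does not rest the case for repair on the first six months. Section 8 expects advantages especially in the longer term and describes harvest morbidity lasting at least two years. Section 5 lists stability and osteoarthritis alongside recovery, and the trial is powered for KOOS-4 at 24 months. Appendix 2 advises against sport-specific training before 6 months and unrestricted sport before 9 months, so a faster return to sport falls where the 6- and 12-month visits can detect it. Early resource use, physiotherapy sessions, complications, and work and study absence are collected by questionnaire or from records and feed the costs, although lost earnings would count mainly in the societal sensitivity analysis. Early pain has its own analysis in section 23.3.2. All of this stands, and it limits the point.

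A reader might go further and infer that the arms are most expected to differ in the first six months, or that the 3- and 6-week contacts exist because an early difference is expected. The documents support neither. Section 5 links pain measurement to the priorities of the patient focus groups, and no section states an expected early utility difference.

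The reply does not remove the gap itself. Faster recovery is still a stated advantage, QALYs are still the primary economic outcome, and cost data do not substitute for utilities.

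**Conclusion.** The point holds as a limited weakness of the measurement schedule. Under linear interpolation, a utility difference that has gone by month 6 contributes zero expected incremental QALY. One that lasts longer is captured in part, at about 53% to 72% in the shapes tried. It would be wrong to conclude that the QALY comparison cannot register any early benefit, or that the economic result would rest on costs alone: the first holds only for a gap closed by month 6, and any difference present at 6, 12 or 24 months enters the QALY.

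The zero follows from the schedule and the pre-randomisation baseline. The £150 to £750 per patient (half that if the gap closes by week 13) depends wholly on an assumed peak gap of 0.03 to 0.10 and an assumed linear shape, and is an illustration, not an estimate. Nothing in the protocol is contradictory here, and the KOOS-4 primary analysis and the sample size are untouched. This is a cheap improvement to the economic evaluation.

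**What to change.** Add the EQ-5D-5L (five items plus the VAS) to the 6-week contact already made with every participant, and optionally to the 3-week contact. Amend Table 1, section 9.3 and section 24 so that the new time point enters the QALY calculation, and align the description in section 17.2.2.

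Pre-specify a sensitivity analysis on the interpolation between week 6 and month 6, for example with the gap closing by week 13 instead of week 26, or with the QALY computed without the 6-week point. This is needed because the 6-week value alone can overstate the gain about twofold if the gap closes by 3 months. A measurement near 3 months would settle that question, but it needs a new contact and is optional.

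The cost is one short instrument on an existing link or postal form and an amendment. The downsides are a slightly longer 6-week form, possibly a slightly lower response to it, and a QALY that depends on the interpolation assumption after week 6. Anyone already past week 6 when the change takes effect will lack the new value, and the health economic analysis plan should say how that is handled.
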